#### 10.3.3. PSA Screening

PSA levels will be recorded as a continuous level (ng/ml). This variable will be dichotomised, using established thresholds (see Section 8.2), into raised ( $\geq 3.0$ ng/ml) and normal ( $< 3.0$ ng/ml) PSA levels.

#### 10.3.4. Clinically Significant/Insignificant and No Cancer

The thresholds for the type of cancer detected are calculated using the Gleason Score, maximum cancer core length (MCCL), and the definitions outlined in Section 8.1 separately.

Imperial Clinical Trials Unit	STATISTICAL ANALYSIS PLAN	PROSTAGRAM
-------------------------------	---------------------------	------------

### 10.3.5. Biopsy Rates

Biopsy rates will be the recorded number of patients who undergo the systematic prostate biopsy, and who undergo a targeted biopsy (MRI- and/or ultrasound-guided). The systematic biopsy will be carried out for any patient who attains at least one positive screening test (PSA, ultrasound or MRI). A MRI or ultrasound-guided biopsy will be carried out for patients who receive a positive screening result by the respective test.

### 10.3.6. Local or Systemic Treatment

Some patients may undergo definitive local or systemic treatment at follow-up. The procedures included are:

- Active surveillance
- Watchful waiting
- Focal treatment
- Radical prostatectomy
- Radical radiotherapy
- ADT.

### 10.3.7. Biopsy Related Adverse Events

Biopsy related adverse events refer to the recorded occurrences of:

- Infectious complications
- Urinary retention
- Haematuria requiring admission.

### 10.3.8. False Positive Results

The first definition of a false positive result, with histology as reference, is defined as a screen-positive result when prostate cancer is not present on biopsy. Prostate cancer not present on biopsy would indicate no cancer was found (using the definition in Section 8.1.3).

The second definition of a false positive result, with histology as reference, is defined as a screen-positive result when no prostate cancer or pathology grade of Gleason 3+3 is present on biopsy. Similarly to the above definition, prostate cancer not present on biopsy would indicate no cancer was found (using the definition in Section 8.1.3).

### 10.3.9. Screening Test Preference (PBQ)

Screening test preference, as measured by PBQ (see Appendix 1), will be dichotomised in four ways, to generate four preference variables:

- Prefer PSA vs any other response
- Prefer MRI vs any other response
- Prefer ultrasound vs any other response
- No preference vs any other response.

## 10.4. Safety Variables

The frequency and incidence of adverse events (AEs) and serious adverse events (SAEs) occurring through the course of the study will be assessed.

An adverse event (AE) is any untoward medical occurrence in a patient or clinical trial subject. AEs will be recorded as any unfavourable and unintended sign or symptom, whether or not they are considered to be related to the trial protocol.

Serious adverse events (SAEs) will be recorded throughout the study. An SAE is defined as any event that

- Results in death;

Imperial Clinical Trials Unit	STATISTICAL ANALYSIS PLAN	PROSTAGRAM
-------------------------------	---------------------------	------------

- Is life threatening\*;
- Requires hospitalisation or prolongation of existing inpatient's hospitalisation\*\*;
- Results in persistent or significant disability or incapacity;
- Is a congenital abnormality or birth defect.

\* "Life-threatening" in the definition of "serious" refers to an event in which the subject was at risk of death at the time of the event; it does not refer to an event which hypothetically might have caused death if it were more severe.

\*\* "Hospitalisation" means any unexpected admission to a hospital department. It does not usually apply to scheduled admissions that were planned before study inclusion or visits to casualty (without admission).

Expected adverse events are listed in Appendix 3.

All protocol deviations and violations will be recorded throughout the study, and reported.

Imperial Clinical Trials Unit	STATISTICAL ANALYSIS PLAN	PROSTAGRAM
-------------------------------	---------------------------	------------

## 11. Statistical Analysis Plan for Primary Outcome Paper

### 11.1. Primary Outcome Paper End Points

Analyses of the following end points will be reported in the primary outcome paper.

#### 11.1.1. Baseline Demographics

Patient characteristics will be summarised. Summaries of continuous variables will be presented as means and standard deviations if normally distributed, and as medians and inter-quartile ranges for skewed data; categorical variables will be presented as frequencies and percentages.

The CONSORT diagram (Section 5.5.1) will display subject disposition throughout the trial.

#### 11.1.2. Primary End Point

The proportions of men with a screen-positive MRI defined by a score of 3 or greater (Likert and PIRADS).

#### 11.1.3. Other Test Performance (MRI and US) End Points

- The proportions of men with screen-positive MRI defined by a score of 4 or greater (Likert and PIRADS)
- The proportion of men with screen-positive prostate ultrasound defined by a score of 3 or greater (US)
- The proportion of men with screen-positive prostate ultrasound defined by a score of 4 or greater (US)
- The proportion of men with raised PSA result defined by a recorded level of 3 ng/mL or greater
- The proportion of participants within each MRI score or US score of 1, 2, 3, 4 or 5
- An evaluation of proportion of participants across each MRI and US score with no cancer, insignificant cancer and significant cancer for each test
- The proportion of participants across each PSA level (raised or normal) with no cancer, insignificant cancer and significant cancer
- A comparison of the proportion of participants with a positive result for each screening test. A comparison of the proportion of men subsequently diagnosed with a clinically significant prostate cancer as defined by pre-specified histological definitions
- Comparison of different testing combinations in terms of biopsy rates, detection of insignificant cancer and significant cancers
- The proportion of men who go onto definitive local or systemic treatment.

#### 11.1.4. Feasibility End Point

- Assess the acceptability of each diagnostic test measured with EBQ, PBQ, and time taken to complete each screening test.

#### 11.1.5. Other End Point

- Rates of biopsy related adverse events (infectious complications, urinary retention, and haematuria requiring admission).

### 11.2. Statistical Methodology

#### 11.2.1. End Point Analysis Summary

All statistical tests will be two-tailed with 5% significance level.

Proportions will be reported as frequencies and percentages, along with the corresponding 95% confidence intervals. Continuous variables will be presented as means and standard deviations if

Imperial Clinical Trials Unit	STATISTICAL ANALYSIS PLAN	PROSTAGRAM
-------------------------------	---------------------------	------------

normally distributed, and as medians and inter-quartile ranges for skewed data; categorical variables will be presented as frequencies and percentages.

The primary end point analysis will be repeated for all cut-offs defining screen-positive MRI and ultrasound, as described in Sections 10.3.1 and 10.3.2.

Only the cut-offs for screen-positive MRI defined by PIRADS (see Section 10.3.1) will be used in the analyses of the other test performance (MRI and US) end points. These analyses will not be repeated for the cut-offs defined by the Likert scoring system.

Analysis of type of clinical cancer detected by the screening tests will be repeated for all definitions of the type of clinical cancer detected as outlined in Section 8.1, with the exception of the HDP analyses which will only be carried out for definitions (i) in Sections 8.1.1 & 8.1.2.

**Table 1: Primary Outcome Paper End Point Analysis**

	End Point	Analysis	Population
Primary End Point			
	Proportions of men with a screen-positive MRI defined by a score of 3 or greater (PIRADS and Likert)	Proportion with positive MRI score defined by a cut-off $\geq 3$ (PIRADS cut-off [1] and Likert cut-off [1] in Section 10.3.1)	Participants with MRI results 
Other Test Performance (MRI and US)			
	Proportions of men with a screen-positive MRI defined by a score of 4 or greater (PIRADS and Likert)	Proportion with positive MRI score defined by a cut-off $\geq 4$ (PIRADS cut-off [2] and Likert cut-off [2] in Section 10.3.1)	Participants with MRI results 
	Proportion of men with a screen-positive prostate ultrasound defined by a score of 3 or greater (US)	Proportion with positive ultrasound score defined by a cut-off $\geq 3$ (US cut-off [1] in Section 10.3.2)	Participants with ultrasound results 
	Proportion of men with a screen-positive prostate ultrasound defined by a score of 4 or greater (US)	Proportion with positive ultrasound score defined by a cut-off $\geq 4$ (US cut-off [2] in Section 10.3.2)	Participants with ultrasound results 
	Proportion of men with raised PSA level (defined as PSA $\geq 3.0\text{ng/mL}$ )	Proportion with raised PSA level (Section 10.3.3)	Participants with PSA results 
	Proportion of participants within each MRI score or US score of 1, 2, 3, 4 or 5	
 
Proportion within each value of Likert score
 
Proportion within each value of PIRADS score
 
Proportion within each value of US score
 
Histograms of distribution of each score (Likert, PIRADS and US) (Sections 10.3.1 & 10.3.2)
 
	Participants who completed the relevant test for the respective analyses 
	Proportion of participants across each MRI and US score with no cancer, insignificant cancer and significant cancer for each test	
 
Proportion within each value of Likert score detected to have each type of clinical cancer (Sections 8.1 & 10.3.1)
 
Proportion within each value of PIRADS detected to have each type of clinical cancer (Sections 8.1 & 10.3.1)
 
	Participants biopsied, and who completed the relevant test for the

Imperial Clinical Trials Unit	STATISTICAL ANALYSIS PLAN	PROSTAGRAM
----------------------------------	---------------------------	------------

	
 
Proportion within each value of US score detected to have each type of clinical cancer (Sections 8.1 & 10.3.2)
 
Histograms of distribution of type of cancer detected across scoring systems
 
	respective analyses 
Proportion of participants with raised and normal PSA level with no cancer, insignificant cancer and significant cancer	Proportion with raised and normal PSA result detected to have each type of clinical cancer (Sections 8.1 & 10.3.3)	Participants biopsied, and who have PSA results 
Comparison of the proportion of participants with a positive result for each screening test	
Comparisons of proportions of results (positive/negative) between pairs of screening tests:
 
 
MRI & ultrasound
 
MRI & PSA
 
Ultrasound & PSA
 
 
using McNemar chi square tests
	Participants who completed both tests in each pair 
Comparison of the proportion of men subsequently diagnosed with a clinically significant prostate cancer (as defined by pre-specified histological definitions)	
 
Sensitivity and specificity of screening results (MRI, ultrasound and PSA) with histology results as reference standard (Sections 10.3.1, 10.3.2 and 10.3.3)
 
Graph displaying proportions of results for each screening test compared to histology results
 
Proportions of false positive results by each screening test (MRI, ultrasound and PSA), using histology (no cancer) as the reference
 
Proportions of false positive results by each screening test (MRI, ultrasound and PSA), using histology (no cancer or Gleason 3+3) as the reference
 
	Participants biopsied, and who completed the relevant test for the respective analysis 
Comparison of different testing combinations in terms of biopsy rates, detection of clinically insignificant cancer and significant cancers	
 
Hypothetical diagnostic pathways (HDP) of the different testing combinations being analysed (Section 8.3): 
 
MRI
 
Ultrasound
 
PSA (<math>\geq 1.0\text{ng/ml}</math>) & MRI
 
PSA (<math>\geq 3.0\text{ng/ml}</math>) & MRI
 
PSA & ultrasound
 
Ultrasound & MRI
 
PSA & ultrasound & MRI
 
 
 
For each HDP, summary statistics for the population of patients with all positive tests, in terms of: 
 
Total number biopsied (Section 10.3.5)
 
Total number detected to have clinically insignificant cancer
 
 
 
	Participants biopsied, and who completed the relevant test for the respective analysis 

Imperial Clinical Trials Unit	STATISTICAL ANALYSIS PLAN	PROSTAGRAM
-------------------------------	---------------------------	------------

	(Section 8.1.2), in targeted and non-targeted cores	
	
 
Total number detected to have clinically significant cancer (Section 8.1.1), in targeted and non-targeted cores
 
	
Proportion of men who go onto definitive local or systemic treatment.	Proportion who undergo each treatment: 
 
Active surveillance
 
Watchful waiting
 
Focal treatment
 
Radical prostatectomy
 
Radical radiotherapy
 
ADT
 
	Participants with positive screening results, by each screening test 
Feasibility		
Assess the acceptability of each diagnostic test measured with EBQ, PBQ and time taken to complete each screening test	
 
EBQ and PBQ Questionnaires (see Appendix 1 for details):             
 
Summary statistics for overall scores for EBQ and PBQ, for each screening test                 
 
Paired t-tests comparing mean overall scores between pairs of screening tests (MRI & PSA, MRI & ultrasound, ultrasound & PSA), for EBQ and PBQ separately
 
Paired t-tests comparing mean difference between pre- and post-screening test scores, for each screening test
 
 
 
Proportions within each value of the Likert score, for each EBQ component, for each screening test (Appendix 1)
 
Mean score for each EBQ component, for each screening test                 
 
Paired t-tests comparing mean component scores between pairs of screening tests (MRI & PSA, MRI & ultrasound, ultrasound & PSA)
 
 
 
Proportions within each value of the Likert score, for each PBQ component, for each screening test (Appendix 1)
 
Mean score for each PBQ component, for each screening test                 
 
Paired t-tests comparing mean component scores between pairs of screening tests (MRI & PSA, MRI & ultrasound, ultrasound & PSA)
 
 
 
 
 
	Participants who completed the relevant test for the respective analyses   For the paired tests, participants who completed both tests in each pair

Imperial Clinical Trials Unit	STATISTICAL ANALYSIS PLAN	PROSTAGRAM
-------------------------------	---------------------------	------------

		
 
• Bar charts displaying the proportions of participants who selected each Likert score, compared between screening tests, for each EBQ & PBQ component
 
• Paired t-tests comparing mean difference between pre- (EBQ) and post- (PBQ) screening test component scores, for each screening test
 
• Proportion of preference for each test as measured by EBQ (expected preference) and PBQ (final preference)
 
• Multivariable logistic regression on dichotomised test preference, for each screening test, controlling for patient related factors
 
• Summary statistics for the time taken for each test to be completed
 
• Proportion who undergo repeat screening assessments (MRI, ultrasound & PSA)
 
• Summary statistics of incidental findings
 
	
Other			
	Rates of biopsy related adverse events (infectious complications, urinary retention, and haematuria requiring admission)	Table of biopsy related adverse events (Section 10.3.7)	Participants who were biopsied 
Subgroup Analysis			
	Proportion of men with a screen-positive MRI defined by a score of 3 or greater (PIRADS)	
 
• Logistic regression model for MRI result (defined using PIRADS cut-off [1], see Section 10.3.1) on age
 
• Ordinal logistic regression model for PIRADS score on age
 
• Boxplots displaying the distribution of age across PIRADS scores
 
	Participants with MRI results 
	Proportion of men with a screen-positive MRI defined by a score of 4 or greater (PIRADS)	Logistic regression model for MRI result (defined using PIRADS cut-off [2], see Section 10.3.1) on age	Participants with MRI results 
	Proportion of men with a screen-positive prostate ultrasound defined by a score of 3 or greater (US)	
 
• Logistic regression model for ultrasound result (defined by US cut-off [1], see Section 10.3.2) on age
 
• Ordinal logistic regression model for US score on age
 
• Boxplots displaying the distribution of age across US scores
 
	Participants with ultrasound results 
	Proportion of men with a screen-positive prostate ultrasound defined by a score of 4 or greater (US)	Logistic regression model for ultrasound result (defined by US cut-off [2], see Section 10.3.2) on age	Participants with ultrasound results 
Interobserver Agreement for MRI			

Imperial Clinical Trials Unit	STATISTICAL ANALYSIS PLAN	PROSTAGRAM
----------------------------------	---------------------------	------------

	Interobserver agreement for double reported MRI scans	
 
• Agreement of PIRADS scores for MRI scans between local and central readers 
 
• Cohen's Kappa statistic
 
 
 
	Participants whose MRI results were double reported  Double reported MRI scans
--	---	---	---

This population will satisfy the definition in Section 9.1

The use of parametric methods of analysis require stronger distributional assumptions. These can be evaluated for robustness using non-parametric methods. Firstly, an appropriate transformation will be considered if the assumption of normality is not met. This may involve a log transformation which provides transparent interpretation of effects in relative terms. Then, non-parametric methods will be considered and implemented if after an appropriate transformation the assumption of normality is still not met.

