2.2 Other test performance objectives (MRI and US)

1. To determine the prevalence of positive test rate of prostate ultrasound in the general male population aged 50 to 69 years
2. To determine the distribution of MRI and US scores in a screened population
3. To evaluate a suitable threshold score that defines positivity of MRI or US in a screening population
4. To estimate the overall agreement between PSA, US and MRI in the proportion of men with a positive result. Then to compare the overall agreement in proportion of men diagnosed with clinically significant prostate cancer on biopsy.

IP1 - PROSTAGRAM	Protocol No: 18HH4595	Sponsor: Imperial College London	V 1.2 01MAY2019
-------------------------	---------------------------------	--	------------------------

5. To explore combinations and sequences of prostate MRI, US and PSA that might be an optimal screening strategy to evaluate in a future definitive study
6. To estimate the overall agreement of Imaging findings, PSA and DRE
7. To report the clinical outcomes of men with a positive PSA, US and/or MRI result

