### 4.2. Secondary End Points

#### 4.2.1. Other Test Performance End Points (MRI and US)

1. The proportions of men with a screen-positive MRI defined by a score of 4 or greater (Likert and PIRADS)
2. The proportion of men with screen-positive prostate ultrasound defined by a score of 3 or greater (US)
3. The proportion of men with screen-positive prostate ultrasound defined by a score of 4 or greater (US)
4. The proportion of men with raised PSA result defined by a recorded level of 3 ng/mL or greater
5. The proportion of participants within each MRI score or US score of 1, 2, 3, 4 or 5
6. An evaluation of proportion of participants across each MRI and US score with no cancer, insignificant cancer and significant cancer with each test
7. The proportion of participants across each PSA level (raised or normal) with no cancer, insignificant cancer and significant cancer
8. A comparison of the proportion of participants with a positive result for each screening test. A comparison of the proportion of men subsequently diagnosed with a clinically significant prostate cancer as defined by pre-specified histological definitions
9. Comparison of different testing combinations in terms of biopsy rates, detection of insignificant cancer and significant cancers
10. The correlation between imaging findings and DRE
11. The proportion of men who go onto definitive local or systemic treatment.

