#### 11.2.3. Other Test Performance (MRI and US) End Point Analysis

The proportion of men with a screen-positive MRI defined by a score of 4 or greater will be reported. This analysis will be repeated for PIRADS cut-off [2] and Likert cut-off [2], as defined in Section 10.3.1.

The proportion of men with a screen-positive prostate ultrasound score (US), using the two US cut-offs for a screen-positive result defined in Section 10.3.2, will be reported. Similarly, the proportion of patients with a raised PSA level, using the definition in Section 10.3.3, will be reported.

The proportions of patients within each discrete score of the Likert, PIRADS and US scoring systems (see Sections 10.3.1 & 10.3.2) will be reported. The distribution of patients across the discrete scores will be displayed using a histogram for each scoring system.

The proportions of patients across the discrete values of the scoring systems for MRI and ultrasound detected to have clinically significant cancer, clinically insignificant cancer or no cancer, by each screening test (repeated for each of the thresholds defined in Section 8.1 separately) will be reported. The distribution of the type of cancer detected by each test, using each definition ((i)-(v), Section 8.1), will be displayed using histograms for each scoring system. Similarly, the proportions of patients with raised and normal PSA (see Section 10.3.3) detected to have clinically significant cancer, clinically insignificant cancer or no cancer (repeated for each of the thresholds defined in Section 8.1 separately) will be reported.

Comparisons of proportions of screening results (positive/negative), between pairs of screening tests, (MRI & ultrasound, MRI & PSA, ultrasound & PSA) will be conducted using McNemar chi square tests. McNemar chi square tests will be used to assess whether there is marginal homogeneity of results between pairs of screening tests. The McNemar chi square test statistic and p-value will be reported for each pair of screening results. This analysis will use the screen-positive MRI cut-offs defined by the PIRADS scoring system (see Section 10.3.1), and the screen-positive ultrasound cut-offs defined by the US scoring system (see Section 10.3.2).

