Sensitivity and specificity analysis will be conducted between screening test results and histology results (reference standard). Histology results will be dichotomised into "clinically significant cancer" and "absence of clinically significant cancer" (repeated for each of the threshold definitions in Section 8.1). The following measures of test accuracy will be reported, along with

Imperial Clinical Trials Unit	STATISTICAL ANALYSIS PLAN	PROSTAGRAM
----------------------------------	---------------------------	------------

their 95% confidence intervals: negative predictive value (NPV), positive predictive value (PPV), sensitivity and specificity. Results will be displayed using graphs for each screening test.

The proportions of false positive results will be reported, with histology as reference. This analysis will be repeated for each of the definitions of false positive results outlined in Section 10.3.8.

For each HDP (see Section 8.3) the proportion of participants with all positive tests, along that pathway, will be reported. For each HDP, we will take the population of participants with all positive tests along each pathway and provide summary statistics. Screen-positive results for MRI are defined by PIRADS cut-off [2] in Section 10.3.1. Similarly, screen-positive results for ultrasound are defined by US cut-off [2] in Section 10.3.2. A “positive” PSA result is defined by a raised PSA level ( $\geq 3.0\text{ng/ml}$ ) (see Section 10.3.3). The summary statistics will be in terms of: the total number of patients who were biopsied (see Section 10.3.5), the total number of patients who were detected to have clinically insignificant cancer in targeted and non-targeted cores, separately, and, the total number of patients who were detected to have clinically significant cancer in targeted and non-targeted cores, separately. This analysis will be limited to the generally accepted definitions for the detection of clinically significant and insignificant cancers (definitions (i) in Sections 8.1.1 & 8.1.2) (7), only.

The proportions of patients, with positive test results by each screening test, who go onto local or systemic treatment for prostate cancer (see Section 10.3.6) will be reported. Positive screening test results will be defined using the PSA cut-off in Section 10.3.3, and both PIRADS and US cut-offs in Sections 10.3.1 & 10.3.2.

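### SAP end point 8 is worded as a comparison of significant-cancer diagnosis between tests, but only separate per-test accuracy is planned; pairing is not carried into cancer detection

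*SAP*

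**What the plan says.** SAP 4.2.1, item 8, lists as an end point "A comparison of the proportion of men subsequently diagnosed with a clinically significant prostate cancer as defined by pre-specified histological definitions". The objective behind it (Protocol 2.2, item 4, repeated in SAP 3.2.1) concerns PSA, ultrasound and MRI together: "Then to compare the overall agreement in proportion of men diagnosed with clinically significant prostate cancer on biopsy".

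For that end point, SAP Table 1 in 11.2.1 assigns "Sensitivity and specificity of screening results (MRI, ultrasound and PSA) with histology results as reference standard", a graph per test, and two versions of the false-positive proportion per test. SAP 11.2.3 adds PPV and NPV with 95% confidence intervals. The population is "Participants biopsied, and who completed the relevant test for the respective" analysis, so it is set test by test. Shell Table 1.2.11 has one column per test and cut-off, with no difference, ratio, cross-classification or p-value.

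Pairing does appear elsewhere. For positive and negative results, 11.2.3 states that "McNemar chi square tests will be used to assess whether there is marginal homogeneity of results between pairs of screening tests", in the population "Participants who completed both tests in each pair". The EBQ and PBQ scores are compared by paired t-tests.

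The nearest other analysis is the hypothetical diagnostic pathway (HDP) table (8.3, 11.2.3, Table 1.2.14). It sets out significant and insignificant cancers per pathway with intervals, split by targeted and non-targeted cores.

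**The concern.** An end point worded as a comparison should have an analysis that estimates a difference or ratio. Here the reader gets separate columns of accuracy measures from overlapping sets of men, and has to judge the contrast by eye from one-sample intervals.

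The missing contrast is also the one this design supports best. Protocol 1.4 says the study was not designed to establish the sensitivity and specificity of MRI, because not every man is biopsied. Any positive test leads to biopsy (Protocol 6.6, SAP 8.2). Men negative on both tests of a pair add nothing to either test's count of detected cancers, so the relative comparison does not need their unverified status. Sensitivity, specificity and NPV do need it.

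Protocol 1.4 also says the results will inform a larger paired cohort comparing PSA and MRI. The frequency of discordant cancers is a design input for such a study, and no planned table reports it.

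**Working it through.** **The plan's own figure.** The only stated sample size is for MRI positivity: n = 1.96² P(1−P)/0.05². P = 0.196 gives 242.1, so 243; P = 0.611 gives 365.2, so 366. Both reproduce. No sample size is given for the cancer comparison.

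**Inputs (Protocol 9.1).** Normal PSA 89.6%, raised PSA 10.4%; significant cancer in normal-PSA men 2.20%; MRI sensitivity 74% or 93%, taken by the protocol as equal in both PSA groups. The documents do not give significant-cancer prevalence in raised-PSA men. I assume 10%, 25% and 40%, and that every test-positive man is biopsied.

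**Expected cells, MRI against PSA, N = 366.**

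- Significant cancers in normal-PSA men: 366 × 0.896 × 0.022 = 7.2
- MRI-positive only: b = 7.2 × sensitivity = 5.3 (74%) or 6.7 (93%)
- PSA-positive only: c = 366 × 0.104 × prevalence × (1 − sensitivity)
- Both positive: a = 366 × 0.104 × prevalence × sensitivity

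**Precision.** The difference is (b − c)/N. Paired SE = √(b + c − (b − c)²/N)/N. Ignoring pairing, SE = √(p₁q₁/N + p₂q₂/N), with p₁ = (a + b)/N and p₂ = (a + c)/N. Power is for a two-sided exact McNemar test at 5%, by simulation (Poisson cells, 20,000 runs).

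| MRI sens. | Assumed prev. | b | c | a | Diff. (points) | Paired ± | Unpaired ± | Power |
|---|---|---|---|---|---|---|---|---|
| 74% | 10% | 5.3 | 1.0 | 2.8 | 1.19 | 1.34 | 1.83 | 0.24 |
| 74% | 25% | 5.3 | 2.5 | 7.0 | 0.78 | 1.49 | 2.47 | 0.09 |
| 74% | 40% | 5.3 | 4.0 | 11.3 | 0.38 | 1.63 | 2.95 | 0.04 |
| 93% | 10% | 6.7 | 0.3 | 3.5 | 1.76 | 1.40 | 1.98 | 0.58 |
| 93% | 25% | 6.7 | 0.7 | 8.8 | 1.65 | 1.44 | 2.63 | 0.48 |
| 93% | 40% | 6.7 | 1.1 | 14.2 | 1.54 | 1.48 | 3.14 | 0.39 |

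The unpaired half-width is about 1.4 times (1.83/1.34) to 2.1 times (3.14/1.48) the paired one. At N = 406 the power range is 0.04 to 0.67. With five discordant cancers all in one direction, exact p = 2 × 0.5⁵ = 0.0625; with six, p = 0.031. So at least six are needed for p < 0.05.

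**Why the columns are not enough.** The per-test totals fix b − c but not b + c. Take the fifth row, with totals of 15.6 (MRI) and 9.5 (PSA): b − c = 6.1, while b + c could lie anywhere from 6.1 (every PSA-positive cancer also MRI-positive) to 15.6 + 9.5 = 25.1 (no overlap). The half-width is then between 1.96 × √(6.1 − 6.1²/366)/366 = 1.31 points and 1.96 × √(25.1 − 6.1²/366)/366 = 2.68 points. Only the cross-tabulation settles it.

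**Whether the HDP table fills the gap.** It has MRI alone and ultrasound alone but no PSA-alone pathway. It uses cut-off [2] only and estimates no difference. It counts men by core type, and a man with cancer in both core types can appear in both rows, so the rows cannot simply be added to give the number of men in the both-positive cell.

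**The case against.** A reader might infer that the SAP ignores the paired design, or that no side-by-side view of cancer detection is planned. The documents do not support either. McNemar tests are planned for all three test pairs on positivity, and paired t-tests for EBQ and PBQ. The HDP table sets cancers side by side, and its combined pathways describe men positive on both tests. Table 1.2.9 adds cancers by PSA level. What is missing is narrower: an estimate of the between-test difference in detected cancers.

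A reader might also expect a paired test to show a clear MRI advantage. An assumed split of 12 MRI-only, 2 PSA-only and 10 both would give a difference of 2.7 per 100 with exact p = 0.013. But 12 exceeds the 7.2 significant cancers that the protocol's inputs imply in all normal-PSA men. The protocol notes that the biopsy behind its 2.20% underestimates cancer, but gives no larger figure.

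Two further objections stand and shape the fix. First, each man has one histology result, and the biopsy he receives depends on his imaging. A cancer in a man positive on both PSA and MRI may be found only in MRI-targeted cores, so crediting it to PSA is not straightforward. Second, screen-positive men who decline biopsy have no histology, and both documents anticipate selective withdrawal (Protocol 5.3.2, SAP 7.2).

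It is also fair that this is a secondary end point in a feasibility study. Protocol 1.4 names the prevalence of a positive test, not relative detection, as the estimate the larger study needs.

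**Conclusion.** The point holds in its limited form. End point 8 is worded as a comparison, the analysis assigned to it is one test at a time, and neither the McNemar tests nor the HDP table supplies the paired estimate of cancer detection.

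Under the protocol's inputs and the assumed 10-40% prevalence in raised-PSA men, the MRI-PSA difference is 0.4 to 1.8 percentage points. Its 95% half-width is about 1.3-1.6 points paired, against 1.8-3.1 if pairing is ignored. The ranges rest on equal MRI sensitivity in both PSA groups and complete biopsy of positives. Refusals would make the counts smaller still.

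With power of 0.04-0.58, the comparison should be presented as estimation, not as a test of superiority. The change is worth making but of moderate weight. The primary end point and its sample size are not affected.

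**What to change.** Add to SAP 11.2.3 and Table 1, for MRI-PSA, MRI-ultrasound and ultrasound-PSA, in men who completed both tests of the pair:

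- A cross-tabulation of significant cancers by first test positive only, second test positive only, and both. Use definition (i), with PIRADS and US cut-off [1] leading and cut-off [2] repeated.
- The paired difference per 100 men screened with its 95% CI, and the detection ratio (a + b)/(a + c).
- An exact McNemar p-value as descriptive support only. Because 11.2.1 says "All statistical tests will be two-tailed with 5% significance level", add a sentence that no significance claim rests on these contrasts.
- The number of screen-positive men without biopsy in each cell.
- A label saying that these are cancers in test-positive men, not cancers found by the test, with a split by targeted and non-targeted cores.
- The same layout for insignificant cancer and for cancer-free biopsies.

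The cost is SAP wording and one extra table from data already collected. The downside is small counts and wide intervals, which the text should state.
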